9.2.1.1. Immunocompromised Population

Individuals must meet at least one of the following criteria at index date or in the 12-month baseline period prior to the index date (unless otherwise specified) to be eligible for inclusion in the immunocompromised population. Definitions will be aligned as closely as possible across participant data sources. Definitions may be modified if certain data elements are not available or are incompletely captured in some data sources.

- Diagnosed with a primary immunodeficiency/immune dysregulation disorder, also known as inborn errors of immunity, as defined by the European Society for Immunodeficiencies (ESID) Registry,²⁴ at any point in medical history
- Diagnosed with HIV/AIDS
- Diagnosed with hematologic malignancy (e.g., chronic lymphocytic leukemia, non-Hodgkin lymphoma, multiple myeloma, acute leukemia) with evidence of treatment at any point in medical history
- Diagnosed with solid malignancy with evidence of treatment within the last 5 years
- Diagnosed with rheumatologic/inflammatory conditions (e.g., Sjogren's syndrome, SLE, psoriatic arthritis, rheumatic arthritis, arthritis spondylarthritis, polymyalgia rheumatica, demyelination multiple sclerosis, polymyalgia rheumatica, IBD, autoimmune thyroiditis) and have evidence of treatment with chemotherapy, immune modulators, or high-dose or long-term systemic corticosteroids (>3 months) in the last 12 months
- Solid-organ transplant recipients or islet transplant recipients taking immunosuppressive therapy
- CAR-T-cell therapy or hematopoietic stem cell transplant recipients taking immunosuppressive therapy
- Active treatment with various immunosuppressive agents (e.g., high-dose systemic corticosteroids [20 or more mg of prednisone or equivalent per day when administered for 2 or more weeks] or long term systemic corticosteroid use (>3 months), alkylating agents, antimetabolites, transplant-related immunosuppressive drugs, cancer chemotherapeutic agents classified as severely immunosuppressive, TNF blockers, and other biologic agents that are immunosuppressive or immunomodulatory, active treatment with ATC code L04).

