9.2.1.3. Hepatically Impaired Population

Individuals must have evidence of moderate or severe hepatic impairment, which will be ascertained at index date and in the 12 months before the index date using coded diagnoses and procedures or laboratory values as feasible.

In data sources where laboratory test results are not available, or where there are substantial levels of missingness, individuals will be considered in the target population if they have a diagnosis code that matches the category of moderate or severe hepatic disease according to the CCI revised by Glasheen et al³³ which has been shown to correlate with inpatient admissions and mortality rates. This definition includes but is not limited to:

- Oesophageal varices
- Gastric varices
- Alcoholic hepatic failure
- Toxic liver disease with hepatic necrosis
- Chronic hepatic failure
- Hepatic failure, unspecified
- Hepatic veno-occlusive disease
- Portal hypertension
- Hepatorenal syndrome

In addition, to maximize the inclusion of individuals with moderate or severe hepatic impairment, codes included in the adaptation of the CCI for mild liver disease by Ludvigsson et al²⁵ (e.g., viral hepatitis, autoimmune hepatitis) will be included if they coexist with an ascites code (R18).

In data sources where laboratory results are available (e.g., SIDIAP), severe chronic liver disease can be measured by a MELD score greater than 24.³⁴ The MELD score is calculated using serum bilirubin, serum creatinine, and International Normalized Ratio (INR) by the formula³⁵:

No exact correspondence exists between the Child-Pugh stages and the MELD scores. However, patients with MELD scores equal to or greater than 10 have similar mortality to patients with a Child-Pugh score of less than 10.²⁵ The same score threshold combined with elastography has clear prognosis implications for patients.³⁶ Thus, we propose to include in the study individuals with MELD scores equal to or greater than 10 to include additional individuals with moderate or severe hepatic impairment. Although there have been efforts to derive Child-Pugh scores from electronic healthcare data sources with identifiable rich clinical data,³⁷ those data may not be available in the data sources proposed for this study. PFIZER CONFIDENTIAL

CT24-WI-GL02-RF02 5.0 Non-Interventional Study Protocol Template For Secondary Data Collection Study 01-Aug-2023

```
Page 27 of 72
```

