9.2.2. Exclusion Criteria

Patients meeting any of the following criteria will not be included in the study:

- 1. Have a diagnosis for the specific outcome under study within the 12 months prior to the index date (to distinguish the recording of previous events from true new events) and at any time prior to the index date for diabetes type 1
- 2. Have received any RSV vaccinations during the 12-month baseline period

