9.3.2. Outcome Definitions

9.3.2.1. Safety Outcomes

Outcomes will be defined consistently across the data sources to the fullest extent possible.

Body system/ classification	Adverse event of special interest	Estimated risk window (days) ^a .	Analytic Approach
Autoimmune diseases	Acute disseminated encephalomyelitis	1-42 ^{39, b} .	Cohort/SCRI
	Diabetes mellitus type I	1-365	Cohort
	Guillain-Barré syndrome	1-42 ^{39, b} .	Cohort/SCRI
	Narcolepsy	1-365°.	Cohort
	Thrombocytopenia (idiopathic)	$1-42^{40}$	Cohort/SCRI
	Thrombosis thrombocytopenia syndrome	1-15 ³⁹	Cohort/SCRI
Cardiovascular system ^{d.}	Acute cardiovascular injury	$1-28^{41}$	Cohort
-	Arrhythmia Specific subgroups of patients with atrial fibrillation and supraventricular arrhythmias will be identified for additional analyses	1–365 ^{e. g.}	Cohort
	Coronary artery disease	1–365	Cohort

Table 1List of Select Adverse Events of Special Interest

PFIZER CONFIDENTIAL

CT24-WI-GL02-RF02 5.0 Non-Interventional Study Protocol Template For Secondary Data Collection Study 01-Aug-2023 Page 30 of 72

Body system/	Adverse event of special interest	Estimated risk	Analytic Approach	
classification		window (days) ^a .		
	Heart failure	1–365	Cohort	
	Microangiopathy	1–365	Cohort	
	Myocarditis	1-21	Cohort/SCRI	
	Myocarditis and pericarditis	1-7	Cohort/SCRI	
	Pericarditis	1-14	Cohort/SCRI	
	Stress cardiomyopathy	1-365	Cohort	
Cinculatory		1-303 $1-28^{39, f.}$	Cohort/SCRI	
Circulatory	Coagulation disorders: Disseminated intravascular	1-20	Conort/SCRI	
system				
	coagulation, venous			
	thromboembolism (pulmonary			
	embolism, deep vein thrombosis),			
	thrombotic microangiopathy,			
	cerebral venous thrombosis,			
	thrombotic thrombocytopenia			
	syndrome, ischemic stroke,			
	myocardial infarction, haemorrhage	-		
	Single organ cutaneous vasculitis	1-28 ^{f.}	Cohort/SCRI	
	Thrombocytopenia with venous	1–15	Cohort/SCRI	
	thromboembolism			
Nerves and	Bell's palsy	1-42 ³⁹	Cohort/SCRI	
central nervous	Generalised convulsion	0-42 ^{39, , g.}	Cohort/SCRI	
system	Meningoencephalitis	1-42 ³⁹	Cohort/SCRI	
	Transverse myelitis	1–42 ^{39, b. c.}	Cohort/SCRI	
Respiratory	Acute respiratory distress syndrome	1–365	Cohort	
system				
Skin and mucous	•	1–42	Cohort	
membrane, bone				
and joints system				
Other system	Anaphylaxis	0-1 ^{39, , g.}	Cohort/SCRI	
	Death (any causes)	0–365 ^{, g.}	Cohort	

Table 1 List of Select Adverse Events of Special Interest

Notes:

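### Exclusion 1 lets people with known multiple sclerosis into the transverse myelitis and ADEM analyses, so relapses can be counted as new events and may attenuate the IRR

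*Protocol*

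**What the plan says.** - Protocol 9.2.1.1 gives, as examples of rheumatologic or inflammatory conditions that qualify a person as immunocompromised, "polymyalgia rheumatica, demyelination multiple sclerosis, polymyalgia rheumatica, IBD, autoimmune thyroiditis". The person must also "have evidence of treatment with chemotherapy, immune modulators, or high-dose or long-term systemic corticosteroids (>3 months) in the last 12 months". A separate criterion admits anyone on active immunosuppressive treatment, whatever the diagnosis.
- Protocol 9.3.2.1, Table 1, lists "Acute disseminated encephalomyelitis" and "Transverse myelitis" as outcomes, each with a risk window of days 1 to 42 and each analysed by cohort and SCRI. Note c to the table takes the intervals for transverse myelitis from published work on demyelinating diseases and cranial disorders.
- Protocol 9.2.2, exclusion 1, removes people who "Have a diagnosis for the specific outcome under study within the 12 months prior to the index date". Its stated purpose is "to distinguish the recording of previous events from true new events". Only type 1 diabetes gets a lookback over the whole record.
- Protocol 9.2.1.3 has "Oesophageal varices", gastric varices and portal hypertension among the hepatic qualifying codes. Table 1 ends the 28-day coagulation composite with "myocardial infarction, haemorrhage", without naming a site or cause.
- Protocol 9.3.2.2 leaves the detailed outcome algorithms to the SAP. The limitations in 9.9 do not discuss outcomes that the qualifying disease can itself cause.

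**The concern.** Transverse myelitis and ADEM are demyelinating events, and an episode in a person with established multiple sclerosis can be coded as one of them. Exclusion 1 asks only whether that same code appeared in the past year. A known diagnosis of multiple sclerosis excludes nobody, and neither does transverse myelitis recorded two years earlier. For these two outcomes the exclusion may not achieve its own purpose of separating old disease from new events.

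Propensity weighting can balance the disease between cohorts, but it does not remove the events the disease causes. In the SCRI such events fall in both the risk and the control interval. These outcomes are rare, so a small group with the underlying disease could supply a sizeable share of the counted events. What is at stake is sensitivity to a real signal in an outcome chosen because it is a vaccine-safety concern.

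**Working it through.** **1. The passages side by side.** Enrolled: treated multiple sclerosis. Outcomes: two demyelinating events. Exclusion: same outcome, 12 months. Lifetime lookback: type 1 diabetes only. Nothing in 9.2.2 keeps a relapse of known demyelinating disease out of the count. Whether a relapse is actually counted depends on algorithms that are not shown.

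**2. The plan's own figure.** No study size is given for transverse myelitis, ADEM or haemorrhage. The nearest figure is Guillain-Barré syndrome in Table 2, which has the same 42-day window. With p0 = 0.0000069, IRR 2, two-sided alpha 0.05 and 80% power:

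n per cohort = (1.960 + 0.842)² × (1 + IRR) / [p0 × (IRR − 1)²] = 7.849 × 3 / 0.0000069 = 3,412,557 (with unrounded z-values).

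This matches Table 2. The same formula returns all 24 entries, so the study-size arithmetic is not in question.

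**3. Dilution.** Let d be the share of events in the comparator (unvaccinated cohort, or SCRI control interval) that the pre-existing disease causes. If vaccination leaves those events unchanged and they are equally frequent on both sides:

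observed IRR = d + (1 − d) × true IRR.

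For d = 0.5 and a true IRR of 2: 0.5 + 0.5 × 2 = 1.5.

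The documents do not give d, so a range is shown. The last two columns use the Guillain-Barré rate as a stand-in for new-onset events and a true IRR of 2. Total background risk becomes p0/(1 − d), and power is evaluated at n = 3,412,557.

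| d (assumed) | observed, true IRR 2 | observed, true IRR 3 | observed, true IRR 5 | power, true IRR 2 | n needed, multiple |
|---|---|---|---|---|---|
| 0 | 2.00 | 3.00 | 5.00 | 80% | 1.00 |
| 0.10 | 1.90 | 2.80 | 4.60 | 77% | 1.07 |
| 0.25 | 1.75 | 2.50 | 4.00 | 72% | 1.22 |
| 0.50 | 1.50 | 2.00 | 3.00 | 58% | 1.67 |
| 0.75 | 1.25 | 1.50 | 2.00 | 37% | 3.0 |
| 0.90 | 1.10 | 1.20 | 1.40 | 18% | 7.0 |

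**4. How far d can be pinned down.** Suppose a fraction m of the cohort has multiple sclerosis, with coded-event rate r1 in them and r0 in everyone else. Then d = m·r1 / [m·r1 + (1 − m)·r0]. All three inputs are assumptions. Rates are per 100,000 person-years.

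- m = 0.5%, r1 = 50, r0 = 1: d = 0.25/(0.25 + 0.995) = 0.20.
- m = 1%, r1 = 200, r0 = 1: d = 2/(2 + 0.99) = 0.67.
- m = 3%, r1 = 500, r0 = 0.3: d = 15/(15 + 0.291) = 0.98.

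The spread from 0.20 to 0.98 shows that the size cannot be settled without data.

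**5. Direction.** If relapses have their own rate ratio R, observed IRR = d × R + (1 − d) × true IRR. With d = 0.5 and a true IRR of 2, R = 0.5, 1, 2 and 3 give 1.25, 1.5, 2.0 and 2.5. With no true effect, R = 0.5 and 1.5 give 0.75 and 1.25, away from 1. R differs from 1 if vaccination affects relapses or if its timing depends on them.

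**The case against.** The strongest reply is that the Protocol leaves the algorithms to the SAP, and a specific algorithm could rule out events in people with known multiple sclerosis. That stands as a limit: a reader might infer that relapses will be counted, but the Protocol shows only that no stated rule stops it. Eligibility, however, is fixed in 9.2.2, which already holds one outcome-specific lookback.

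A second reply is that the objective concerns safety in these very populations, so events in people with multiple sclerosis belong in the answer. This also stands, and is why they should be reported separately rather than dropped.

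A third is that safeguards exist: comparators from the same population, autoimmune disorders as a covariate, narrow and broad algorithms, and subgroup analyses as feasible. These help with balance and may reveal the problem. None removes the dilution, and none is directed at prior demyelinating disease.

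A reader might also infer that variceal bleeds are miscounted in the same way and should be deleted from the haemorrhage component. The documents do not support that. A new variceal bleed is a genuine haemorrhage in a person the study means to cover. Its code list is not shown. Deleting it would give the hepatic population a different composite from the other two, while section 9.7 foresees combining the three.

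**Conclusion.** The gap is real for transverse myelitis and ADEM: the exclusion does not address known demyelinating disease, although treated multiple sclerosis is a named route into the study. Attenuation is the likely result if disease-caused events are unaffected by vaccination and balanced. A true IRR of 2 then reads between 1.90 and 1.10 for an assumed d of 0.10 to 0.90. It would go too far to say that the IRR is necessarily pulled towards 1, because step 5 shows it can move either way. It would also go too far to attach one figure to the bias, since d is not in the documents. The point is a worthwhile and inexpensive improvement; it does not show that the analysis as planned is invalid. For variceal bleeding only a sensitivity analysis is justified.

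**What to change.** 1. In Protocol 9.2.2, beside the type 1 diabetes rule, add for the transverse myelitis and ADEM analyses (cohort and SCRI) a lookback over all available history for multiple sclerosis or other demyelinating disease. Take those people out of the main estimate and report them as a separate stratum, so that relapse safety stays visible.
2. In 9.7.4, add for the hepatically impaired population a sensitivity analysis that reports variceal and portal-hypertensive bleeding separately and repeats the coagulation composite without it. Keep these bleeds in the main composite. Because 9.7.2 ends composite follow-up at the first component, the repeat should let follow-up continue past such a bleed.

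The cost is a few lines and matching code lists. No new kind of data is needed, since 9.2.1.1 already uses any-time history for some conditions. The main estimates for the two outcomes would no longer cover the few people with prior demyelinating disease. The lookback also reaches only as far as each data source's record, as it does for type 1 diabetes.

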9.2.1.2. Renally Impaired Population

Individuals must have evidence of moderate or severe renal impairment, ascertained at index date or in the 12 months before index date using coded diagnoses and procedures or laboratory values as feasible.

In data sources where laboratory results are not available or where there are substantial levels of missingness, individuals with diagnosis codes that identify severe and moderate renal disease as part of the CCI by Ludvigsson et al²⁵ will be used. This includes but is not limited to:

PFIZER CONFIDENTIAL CT24-WI-GL02-RF02 5.0 Non-Interventional Study Protocol Template For Secondary Data Collection Study 01-Aug-2023 Page 25 of 72

- Hypertensive renal disease with renal failure
- Hypertensive heart and renal disease with renal failure
- Chronic nephritic syndrome
- Chronic tubulo-interstitial nephritis
- Chronic kidney disease (CKD)

Patients will be included in the renally impaired cohort if they have 2 different occurrences of those codes separated by at least 90 days in the baseline period. ICD-10 codes will be adapted to the specific disease coding system used in each data source.

In data sources where laboratory results are available (e.g., SIDIAP), individuals will also be included in the renally impaired cohort if:

- They have 2 eGFR test results < 60 mL/min/1.73 m²—taken from Levey et al²⁶ separated by at least 90 days (with no normal values in between) but not more than 540 days OR
- They have 2 UACR results \geq 30 mg/g separated by at least 90 days (with no normal values in between) and no more than 540 days (severe albuminuria)

Definitions for CKD stages are based on the KDIGO guidelines.^{26, 27} Currently, albuminuria levels are also used to stratify levels of renal impairment.²⁷ The 3 microalbuminuria categories add prognostic information on renal and cardiovascular complications to the eGFR categories. However, patients in eGFR categories 1 and 2 (eGFR \ge 60 mL/min/1.73 m2) and moderate albuminuria have a different clinical profile and normal to moderately increased risk of complications. Therefore, among patients with eGFR \ge 60 mL/min/1.73m² only the patients with severe albuminuria will be considered. A potential limitation of using UACR test results is that clinicians use dipstick measurements as the main method of assessing UACR, and dipstick measurements are not captured in most data sources.

The eGFR will be defined using eGFR as recorded in the data source either by diagnosis codes or laboratory results as feasible. If eGFR is not recorded in the data source, it will be derived from creatinine levels using the 2021 CKD-EPI equation,²⁸ which removes the race-related coefficient, following recommendations from recent evidence and guideline statements.²⁹⁻³² The CKD-EPI equation is as follows:

$$eGFR = 142 \times \min(\frac{Scr}{\kappa}, 1)^{a1} \times \max(\frac{Scr}{\kappa}, 1)^{a2} \times c^{Age} \times d$$
 (if female)

Where:

Scr is serum creatinine concentration;

a1 = -0.241 for females and -0.302 for males;

a2 = -1.200; c = 0.9938; d = 1.012;

 κ is 0.7 for female participants and 0.9 for male participants;

min indicates the minimum of Scr/ κ and 1, and max indicates the maximum of Scr/ κ and 1.

PFIZER CONFIDENTIAL

CT24-WI-GL02-RF02 5.0 Non-Interventional Study Protocol Template For Secondary Data Collection Study 01-Aug-2023 Page 26 of 72 The exponent a1 is used for levels of creatinine $\leq 0.9 \text{ mg/dL}$ for male participants and $\leq 0.7 \text{ mg/dL}$ for female participants, and the exponent a2 is used for levels of creatinine > 0.9 mg/dL for male participants and > 0.7 mg/dL for female participants.

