9.1.1. Primary Design - Comparative Cohort Design

A comparative cohort design will be used to estimate incidence rates and incidence rate ratios of prespecified outcomes among immunocompromised, or renally impaired, or hepatically impaired older adults with and without receipt of the ABRYSVO vaccine. Individuals in the unvaccinated cohort must have no record of an RSV vaccine on the index date or in the baseline period prior to index date or any other vaccine on the index date but can later receive ABRYSVO and enter the vaccinated cohort if all eligibility criteria are met. To address possible selection bias due to health seeking behaviours, unvaccinated individuals will be randomly selected from a population of patients who have regular use of preventive medical care, defined as at least one vaccination record in the year prior to the index date. The baseline period is defined as 12 months prior to the index date. The follow-up period will begin from day 1 (the day after ABRYSVO administration for vaccinated cohort, or the day after matched index date for the unvaccinated cohort) and continue to the earliest occurrence of an outcome, date of RSV vaccination (for unvaccinated individuals who later receive any RSV vaccine only), the end of administrative follow-up, end of the study period, or death. For those outcomes with a defined risk window, follow-up will also be truncated at the end of the risk window. To enhance comparability between the vaccinated and unvaccinated cohorts, ATT weights will be used. Weights, based on PS, will incorporate additional measures of healthcare utilization in the baseline period to further account for potential differences in healthcare seeking behaviour between the vaccinated and unvaccinated cohorts. However, as this study focuses on patients with chronically managed conditions, differences in healthcare seeking behaviour are not anticipated. IPCW will also be employed if informative censoring (i.e., differential rates of censoring during follow up) and high censoring rates are observed between the vaccinated and unvaccinated cohorts. Examples of patient follow-up scenarios are depicted in Figure 1 and Figure 2. Comparative analyses will also include variables that remain inadequately balanced between the two cohorts in a doubly robust approach. Further details are provided in Section 9.7.2 and Section 9.7.3.

Figure 1 Comparative Cohort Design

[figure not shown]

Notes:

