9.2.1. Inclusion Criteria

Patients meeting the following criteria will be included in the study:

- Vaccinated Cohort: Vaccination with ABRYSVO
- *Unvaccinated Cohort:* No vaccination with ABRYSVO or other vaccines on the index date
- *Unvaccinated Cohort:* No vaccination with any RSV vaccine in the 12-months prior to index
- Each population of immunocompromised or renally impaired or hepatically impaired individuals must meet the population-specific inclusion criteria in Section 9.2.1.1, Section 9.2.1.2, and Section 9.2.1.3, respectively
- Age 60 years and older at index date
- A minimum of 12 months of administrative enrollment history prior to index in one of the selected data sources to ensure adequate characterisation of medical history
- A minimum of one day of follow up post-index
- For analyses of outcomes assessed with the SCRI design, the following additional criteria must be met. Note that the study population for each outcome-specific analysis will thus be different
 - a. Have received ABRYSVO
 - b. Have experienced an event of interest during the risk or control interval
 - c. Have full accrual of data used to define the event in the risk and control intervals combined, after accounting for any data lag and timing of data extraction

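### The laboratory routes into the renally impaired cohort conflict with section 9.2.1.2's own 12-month window and severe-only albuminuria rule

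*Protocol*

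**What the plan says.** Protocol section 9.2.1.2 limits the cohort to people whose renal impairment is at least moderate, with status to be "ascertained at index date or in the 12 months before index date using coded diagnoses and procedures or laboratory values as feasible". Section 9.1.1 fixes the reference window: "The baseline period is defined as 12 months prior to the index date". Section 9.2.1 sets the matching enrolment requirement: "A minimum of 12 months of administrative enrollment history prior to index in one of the selected data sources".

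There are three ways into the renal cohort:

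- **Diagnosis codes.** Two code occurrences at least 90 days apart, both within the baseline period.
- **eGFR**, where results exist. Two results below 60 mL/min/1.73 m², "separated by at least 90 days (with no normal values in between) but not more than 540 days OR" the UACR route.
- **UACR**, where results exist. Two results of 30 mg/g or more, again spaced by 90 days or longer, "with no normal values in between) and no more than 540 days (severe albuminuria".

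The paragraph after these bullets refers to three albuminuria categories without giving their cut-points. It says that people with eGFR of 60 or above and "moderate albuminuria have a different clinical profile and normal to moderately increased risk of complications". It concludes that, in that eGFR range, "only the patients with severe albuminuria will be considered".

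**The concern.** Two parts of one short definition do not fit together.

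First, the window and the spacing cannot both be applied in full. The window explicitly covers laboratory values, and the allowed spacing is longer than the window. This affects the eGFR route as well as the UACR route.

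Second, the UACR bullet gives one number, labels everything at or above it severe, and contrasts it with normal values. The following paragraph depends on a moderate category lying between the two. People with persistent eGFR below 60 already qualify through the eGFR bullet. The UACR bullet therefore mainly adds people with eGFR of 60 or above, the group that the severe-only sentence is meant to restrict.

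What is at stake is whom the renal estimates describe. The primary objective includes absolute incidence rates as well as rate ratios, in a population that section 7 says was absent from the supporting trials. Sections 9.4.1 to 9.4.4 describe laboratory data in four of the five sources; section 9.4.5 says SNDS has no results. If the laboratory routes admit people whom the protocol regards as outside the target, or lose people whom it wants, the renal cohort will differ between laboratory and code-only sources before the meta-analysis in section 9.7.3.3. Extraction is local (section 9.6.1) and analysis scripts are central (section 9.6.2). A look-back that is not stated may therefore not be extracted.

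**Working it through.** The plan attaches no figure of its own to this definition, so there is none to reproduce. The sample sizes in Table 2 do not depend on it.

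**(a) Window against spacing**

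Inputs: 12-month window (sections 9.1.1 and 9.2.1.2), taken as 365 days; permitted spacing 90 to 540 days (both laboratory bullets in 9.2.1.2).

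- Largest spacing of two results that both lie in the window: 365 days.
- Excess of the permitted maximum over the window: 540 − 365 = 175 days.
- Whole-day spacings permitted: 540 − 90 + 1 = 451.
- Permitted spacings that cannot occur inside the window (366 to 540): 175.
- Share of the permitted range: 175/451 = 38.8%.
- If the 12 months include a leap day (366 days): 540 − 366 = 174, and 174/451 = 38.6%.

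This is a share of calendar gaps. It says nothing about the share of patients, which depends on testing intervals that the protocol does not give.

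The surrounding text offers no exception. Section 9.2.1.1 (immunocompromised) allows stated departures from its 12-month window; section 9.2.1.2 has no such clause. Its diagnosis-code route explicitly keeps both codes within baseline.

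**(b) UACR threshold against label and restriction**

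| Element of 9.2.1.2 | What it implies |
|---|---|
| Threshold 30 mg/g, no upper bound, no eGFR condition | Anyone with two qualifying results enters, whatever the eGFR |
| Label on the bullet | All of these people count as severe |
| Contrast with normal values between the two results | The cut reads as normal against abnormal |
| Next paragraph: three categories, moderate distinct from severe | Something must lie between normal and severe |
| Next paragraph: at eGFR 60 or above, severe only | Moderate must be identifiable in order to be left out |

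Rows 1 to 3 leave two groups, normal and severe. Rows 4 and 5 need a third. A program that codes the printed number and label treats everyone who meets the bullet as severe. The restriction in row 5 then removes nobody.

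**The case against.** **A workable reading of the window exists.** The laboratory bullets omit the baseline-period phrase used for diagnosis codes and set their own spacing. One can read them as requiring only the later result in the 12 months, with the earlier one as confirmation. That is sensible, but the text does not say it, and the opening sentence of the section names laboratory values. A request for clarification stands.

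**The UACR paragraph can be read as restricting the bullet.** Read together, moderate albuminuria at eGFR of 60 or above is excluded in words. This stands as a statement of intent. It cannot be carried out, because the only number printed already carries the severe label.

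**The threshold has not been shown to be wrong.** This also stands. The protocol prints no cut-point between moderate and severe and does not define normal, and the guideline it cites is not at hand. A reader might infer a unit slip, or that most UACR entrants belong to the excluded group. The protocol gives neither the cut-points nor the prevalences needed to support either inference.

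**The study start does not block a longer look-back.** A reader might infer from the 23 August 2022 start that earlier results are unavailable. The protocol does not support this. Section 9.2.1.1 uses unlimited history and a five-year treatment window, section 9.2.2 uses unlimited history for type 1 diabetes, the 12 months of enrolment is a minimum, and SIDIAP holds data since January 2006.

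**The reach is limited.** The laboratory routes only add people; someone tested yearly may still enter through two codes. SNDS is untouched. The section itself notes that dipsticks are the main method and are mostly not captured, which limits entry by UACR alone. Both comparison cohorts use the same definition, so the issue is the population described and not, in itself, bias between cohorts. All of this stands.

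**Conclusion.** The point holds for the two laboratory routes of section 9.2.1.2 and should be corrected before data are extracted. It would be too strong to conclude that the renal cohort as a whole is wrongly defined, because the diagnosis-code route is internally consistent.

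The window conflict follows from the protocol's own figures: with 12 months taken as 365 days, 175 of 451 permitted spacings are unattainable under the stated window. The UACR conflict is between a number, its label and a restriction: as printed, the restriction cannot operate. Which of the three needs changing cannot be settled from the protocol alone. The number of patients affected by either conflict is unknown.

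**What to change.** 1. **UACR.** Check the threshold, value and units, against the guideline the protocol cites. Reconcile it with the severe label and with the severe-only sentence, and tie the severe criterion explicitly to eGFR of 60 or above.
2. **Window, both laboratory bullets.** State that the later result must fall on the index date or in the 12 months before it, and that the earlier one may precede it by 90 to 540 days. Alternatively, cap the spacing at the 12-month window.
3. **Extraction.** Specify the matching laboratory look-back where history exists. Under the first option in item 2 it reaches up to 365 + 540 = 905 days before index; under the cap, 12 months is enough. With only 12 months of enrolment required, say that the earlier result may not be observable for everyone.

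The cost is a few lines of text, possibly a smaller subgroup entering by UACR alone, and a longer laboratory extraction if the first option is chosen.
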